One hundred and fifty treatment seeking alcohol dependent individuals (men and women) will be recruited to participate in this medication study. Subjects may or may not participate in laboratory sessions. Subjects will be recruited through flyers and advertisements in local newspapers and from community substance abuse treatment facilities. Subjects will participate in an initial screening and intake session to obtain informed consent, followed by physical examination and blood work to determine eligibility. Subjects will be randomized to Prazosin (PRZ) or placebo (PLA) and medication will be dispensed in a three times daily dosing schedule (t.i.d. dosing) with 5 mg in the morning, 5 mg in the afternoon and 6 mg at night reached at the end of the 2-week period, and maintained at this or their highest tolerated dose until week 11, followed by a 5-day taper in week 12, as in previous research. The titration schedule was as follows: 1 mg dose at bedtime for 2 nights, followed by a 1mg dose morning and night (8 AM/8 PM) on day 3, then 2 mg dose t.i.d., on days 4-6, 3 mg dose (2 pills each) morning and afternoon, and 4 mg dose (2 pills) at night for days 7-9, increased to 4 mg dosing t.i.d. on days 10-13, and from day 14 through week 11, 5 mg (1 pill) each in the morning and afternoon, and 6 mg for the night (2 pills) dose. Subjects will be maintained on this dose during the laboratory sessions (if completing the laboratory sessions) and until week 12 of the study at which point they will be tapered off the study medication over the course of five days. Some subjects may be tapered prior to completion of the 12 weeks. This taper is similar to what has been used with lofexidine in opiate withdrawal protocols (Bearn et al., 1996; Strang et al., 1997) and in our outpatient relapse prevention study of lofexidine with opiate dependent patients. We expect most subjects will tolerate a daily dose of 16.0mg. However, subjects who cannot tolerate a dosing schedule of 16.0 mg will meet with the study psychiatrist to discuss a reduction in dose down to 10mg/day. Based on the Physician Desk Reference (2007), which reports that dosage may be as high as 40mg daily, we anticipate that 16.0mg per day will be well tolerated by subjects. Subjects who cannot tolerate a minimum dose of 6mg/day will be removed from the study protocol.

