After completing the inpatient phase of the study, subjects will either taper off the study medication or participate in a 9-week outpatient medication trial. Those choosing to continue treatment will be seen 2 times per week in outpatient treatment at the Substance Abuse Center at CMHC, or at the Yale Stress Center at [name]. Subjects will be maintained on 16.0mg dose of PRZ/PLA until week 12. In week 12, subjects will undergo a 5-day taper similar to what has been used with Lofexidine in opiate withdrawal protocols (Bearn et al., 1996; Strange et al., 1997) and in our outpatient relapse prevention study of Lofexidine and Guanfacine with opiate and cocaine dependent patients respectively. Urine monitoring, assessment of craving, alcohol abstinence symptoms, self report of drug use and stress and craving scales, heart rate and blood pressure will be assessed weekly in the trial.

Inpatient-Outpatient Plan without laboratory sessions:

The plan for subjects completing the Inpatient-Outpatient Plan without laboratory sessions, will be identical to the plan for the Inpatient-Outpatient Plan with laboratory sessions, minus the laboratory sessions, and all procedures related to the laboratory sessions, such as participating in imagery script development sessions. Once a subject is deemed eligible, those who are interested in the inpatient option will be admitted to the Clinical Neuroscience Research Unit (CNRU) of

the Connecticut Mental Health Center (CMHC) for the 3 - 4 week stay that will involve medication initiation.

After completing the inpatient phase of the study, subjects will either taper off the study medication or participate in a 9-week outpatient medication trial. Those choosing to continue treatment will be seen 2 times per week in outpatient treatment at the Substance Abuse Center at CMHC, or at the Yale Stress Center at [name]. Subjects will be maintained on 16.0mg dose of PRZ/PLA until week 12.

Outpatient Plan:

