After a subject is able to abstain from substances for a period of 21+ days, they will have the option to complete a 3-night stay on the CNRU, where they will participate in imagery training and 3 laboratory sessions. After completion of the laboratory sessions, subjects will be discharged from the inpatient unit at least one day after the laboratory sessions.

Subjects will undergo the same titration onto study medication as outlined above. If the subject decides to complete the laboratory component, they will be maintained on 16.0mg dose of PRZ/PLA medication during the week of the inpatient laboratory sessions, after which they will undergo the above mentioned taper or continue to take their medication for 9 weeks in outpatient

treatment. In the event that someone continues to use alcohol while in the study, they may be asked to come in for more frequent appointments to assess for adverse symptomatology and meet with the study psychiatrist. Similar methods have been used in our outpatient lofexidine study and no adverse interaction events are anticipated.

Table 1: PRZ/PLA Dosing

	Prazosin PRZ (N = 75) (Male / Female)			Placebo (PLA) (N = 75) (Male / Female)		
Week 1	AM	PM	Evening	AM	PM	Evening
Days 1 -2 (1mg / 1mg)	0mg / 0mg	0mg / 0mg	1mg / 1mg	0mg / 0mg	0mg / 0mg	1mg / 1mg
Days 3 (2mg /1mg)	1mg / 0mg	0mg / 0mg	1mg / 1mg	1mg / 0mg	0mg / 0mg	1mg / 1mg
Days 4-6 (6 mg/4mg)	2mg/1mg	2mg/1 mg	2 mg/2mg	2mg/1mg	2mg/1 mg	2mg/2mg
Week 2						
Days 7-9 (10mg /8mg)	3mg / 2mg	3mg / 2mg	4mg /4mg	3mg / 2mg	3mg / 2mg	4mg /4mg
Days 10 – 13 (12mg/12mg)	4mg /4mg	4mg/4mg	4mg /4mg	4mg /4mg	4mg /4mg	4mg /4mg
Day 14 (16mg/16mg)	5mg/5mg	5mg/5mg	6mg/6mg	5mg/5mg	5mg/5mg	6mg/6mg

Follow-up:

Upon completion of outpatient treatment, follow-up interviews will be scheduled with all subjects. If a subject decides to complete only the inpatient phase, follow-up appointments will be scheduled after the inpatient phase is complete. Follow up interviews will be scheduled at 30 days. Urine monitoring, assessment of craving, cocaine abstinence symptoms, self report of drug use and stress and craving scales, will be assessed during the follow-up appointment.

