Prazosin (marketed by Pfizer) is an alpha-1-adrenergic agonist, that is known to preferentially bind to post-synaptic alpha1-adrenergic receptors that are highly concentrated in the prefrontal cortical regions (Taylor & Raskind, 2002). It has been shown to have beneficial effects on PTSD symptoms (Taylor et al., 2006; Taylor & Raskind, 2000) and recent data has supported it's use in alcohol/cocaine dependence (Simpson et al., in press; Zhang & Kosten, 2005). The major advantage that Prazosin has over clonidine is that it is less sedating and with less hypotensive effects than clonidine. More specifically, Clonidine is a non-selective agonist of alpha 2a, 2 b and 2c receptors, which accounts for its sedative and hypotensive effects. Conversely, Prazosin and guanfacine are preferential for the alpha-1 and alpha-2a receptors respectively; thus, limiting sedative and hypotensive effects (Arnsten et al., 1988). Additionally, the plasma half life of Prazosin is 2-3 hours, compared to 4-10 hours for clonidine (Physician Desk Reference, 2007), allowing rapid titration and limiting accumulation of the drug.

Studies using Prazosin in patients with PTSD and alcohol dependence have used doses ranging from 2 to 16 mg/day. Commonly reported side effects with Prazosin have been fatigue, sedation and light-headedness, which are generally rated as mild in intensity. Possible side effects commonly associated with Prazosin include: low blood pressure, some drowsiness, dryness of mouth and/or throat and dizziness. No serious side effects have been noted in adult populations. There is no evidence that Prazosin will pose a greater risk to the pilot study population. Subjects will not be started on the study medication until no alcohol is present in their system. Throughout the study, subjects will be monitored for alcohol consumption. If a subject were to resume using alcohol, study medication will be discontinued.

iii) Laboratory Sessions:

(a) Intravenous (IV) Catheter: When an IV is started, there is some risk that subjects may develop a bruise or bleeding where the vein is punctured. If this occurs, appropriate treatment will be instituted immediately. On extremely rare occasions, fainting, blood clot or infection may occur.

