with medication and alcohol withdrawal/anxiety, we used a conservative effect size of $d = .60$ for detection of significant main effects and possible interactions in the clinical trial. At this effect size and power = .80, with $p < .05$, sample size estimates from Cohen (1988, p.258) indicated that we would require 25 subjects per cell to adequately assess the proposed hypotheses for the clinical trial (total $N = 100$). Including a 15-20% drop-out after enrollment, we estimated recruitment of 120 AD patients into the trial to ensure adequate power for the trial.

Data Analysis for Laboratory Study: Repeated measures ANOVA and mixed model procedures to assess treatment group differences in alcohol craving and stress related changes (heart rate, blood pressure, HPA and catecholamine responses) during laboratory exposure to stress and drug cues as compared to neutral imagery conditions. Non-parametric tests will be used to assess occurrence of side effects, treatment retention rates, alcohol use measures, CIWA scores and perceived stress scores during the outpatient treatment phase. The number and type of AE's for the two treatment groups will be conducted using t-tests, chi-square tests and ANOVAs as appropriate. Findings will be used to estimate effect sizes for the medication and guide the larger randomized clinical trial.

Data Analysis for the 12-week clinical trial Study: For this phase, the following moderator and primary and secondary outcomes are specified:

Primary Moderator Measure: Alcohol withdrawal symptoms, as measured by the CIWA alcohol withdrawal scale,

Primary Outcome Measures in the outpatient treatment phase: These are: (1) Heavy drinking days (5 or more for men, 4 or more for women) during the 12 week period, and (2) Any drinking days. Both will be assessed daily using smartphone or interactive voice recording surveys completed by the patients and also with weekly urine drug screens/breathalyzer reports and self report of drug use on the Substance Use Calendar.

Secondary Outcome Measures in the outpatient treatment phase: Secondary outcome measures will include alcohol craving scales, anxiety (Hamilton Anxiety Scale) and depression (CES-D) and sleep quality using the Pittsburgh Sleep Quality Index – PSQI).

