Data Analytic Procedures: Since patients will be randomly assigned to the Prazosin and PLA treatment groups and Intent-to-Treat (ITT) analyses will be conducted for the clinical outcomes. We do not expect the groups to be different on demographic, prior drug use history or other predictor variables. Nevertheless, prior to undertaking the specific analysis for each aim, we will compare the treatment groups on demographic variables, substance use characteristics and previous psychiatric history/predictor variables using t-tests/chi-square analyses as appropriate. If any group differences are found, the specific variable will be entered as a covariate in all of the specific analyses. As there are no established thresholds for AW effects on drinking outcomes in outpatient treatment, baseline AW will be assessed as continuous measure in all overall analyses. Thus, intent-to-treat (ITT) analyses with baseline AW severity (mean-centered continuous CIWA-Ar scores) as a moderator of Time (Pre-Full Dose(FD): weeks 1-2; Post FD: weeks 3-12) were conducted with linear or generalized linear mixed effect (LME/GLME) piecewise growth models for continuous and binary outcomes. Due to a positive skew, number of drinks per day

(AvgD) will be log-transformed. Control variables in all analyses will be gender (0=male), inpatient (0=outpatient), and dropout (0=completer, 1=dropout/withdrawn prior to 4 weeks, 2=dropout/withdrawn after 4 weeks). For secondary outcomes linear mixed models with random intercepts will be used to assess the effect of AW, Treatment and Week (factor 1-12, or Weeks 4, 8 and 12) on the secondary outcome variables. All control variables from the main outcome analyses are included in the secondary outcome analyses. If significant interactions with AW are observed for primary or secondary outcome analyses, a median split of AW scores will be conducted to obtain Low and High AW groups and assess contrasts by treatment.

Aims and Hypotheses for Laboratory and Treatment Outcome Components: All analyses of the laboratory and the treatment components will be based on the following specific aims and hypotheses:

Specific Aim 1: To evaluate the effects of Prazosin on stress-induced alcohol craving and associated neuroadaptations in alcohol dependent individuals. Hypothesis 1: Prazosin will decrease stress-induced alcohol craving and negative emotions in the laboratory as compared to placebo.

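### Adverse-event counts are compared between arms with no allowance for unequal, partly treatment-dependent time on study, so the comparison can be biased in either direction.

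*Combined protocol and SAP*

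**What the plan says.** Section V, item 12, Data Analysis for Laboratory Study, contains the only adverse-event analysis. The number and type of events "for the two treatment groups will be conducted using t-tests, chi-square tests and ANOVAs as appropriate". An adjacent sentence adds: "Non-parametric tests will be used to assess occurrence of side effects, treatment retention rates, alcohol use measures". Retention is thus compared between arms but not linked to the event comparison. The paragraph on the 12-week trial names no adverse-event analysis. Data Analytic Procedures lists among its control variables "dropout (0=completer, 1=dropout/withdrawn prior to 4 weeks, 2=dropout/withdrawn after 4 weeks".

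Several rules set how long a patient is on medication or under observation:

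- **Intolerance.** Item 3, Research Plan, first allows a dose reduction, then states: "Subjects who cannot tolerate a minimum dose of 6mg/day will be removed from the study protocol". Section VI.A, item 3 (Source), instead keeps such patients on the highest dose they tolerate.
- **Early taper.** Item 3, Research Plan: "Some subjects may be tapered prior to completion of the 12 weeks".
- **End of the inpatient phase.** After 3-4 weeks, "subjects will either taper off the study medication or participate in a 9-week outpatient medication trial".
- **Drinking.** Item 9 (Risks), Prazosin Treatment: "If a subject were to resume using alcohol, study medication will be discontinued". The Alcohol Detoxification part of item 9 withdraws patients who cannot stay abstinent. Item 3, where relapse is defined, keeps relapsed patients in the protocol.
- **Extra visits.** Under the Outpatient Plan, of patients who keep drinking: "they may be asked to come in for more frequent appointments to assess for adverse symptomatology".

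**The concern.** A t-test on event counts, or a chi-square on event types, treats a patient observed for ten days like one observed for twelve weeks. That does little harm if time on study is the same in both arms. Here it need not be. Intolerance removals would be expected mainly on active drug. Drinking stops, if applied, fall on whichever arm drinks more. Randomisation does not balance exposure that treatment itself changes.

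At stake is the trial's between-arm statement on the tolerability of 16 mg/day. The same paragraph says the findings will inform a larger trial, so a difference in counts that merely reflects a difference in weeks observed, or one hidden by it, would be carried forward.

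**Working it through.** The plan states no event rate, no mean exposure and no power for adverse events, so there is no figure of its own to reproduce. The check asks which way the bias goes and how far.

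**Step 1: model.** With a constant event rate, expected count = rate × weeks. So observed count ratio ÷ true rate ratio = mean weeks on prazosin ÷ mean weeks on placebo. For each arm:

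mean weeks = a × 2 + (1 − a) × [b × 4 + (1 − b) × 12]

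Here a is the share removed for intolerance at week 2 (zero on placebo unless stated) and b the share stopped for drinking at week 4. The values of a and both stop weeks are assumptions. The dosing table reaches 4-6 mg/day on days 4-6, so early removal is possible. For b, the Power Analysis reports pilot abstinence of 6/7 on prazosin and 4/10 on placebo. This gives 1/7 and 6/10 if every non-abstinent patient were stopped.

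**Step 2: intolerance only (b = 0 in both arms).**

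- a = 5%: 0.1 + 0.95 × 12 = 11.5; 11.5/12 = 0.96
- a = 10%: 0.2 + 0.90 × 12 = 11.0; 11.0/12 = 0.92
- a = 20%: 0.4 + 0.80 × 12 = 10.0; 10.0/12 = 0.83

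**Step 3: drinking stops at pilot shares.** Placebo: 0.6 × 4 + 0.4 × 12 = 7.2 weeks. Prazosin before intolerance: (1/7) × 4 + (6/7) × 12 = 10.86 weeks.

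- a = 0: 10.86/7.2 = 1.51
- a = 5%: (0.1 + 0.95 × 10.86)/7.2 = 1.45
- a = 10%: (0.2 + 0.90 × 10.86)/7.2 = 1.38
- a = 20%: (0.4 + 0.80 × 10.86)/7.2 = 1.26

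With equal drinking stops of 30%, both arms start from 0.3 × 4 + 0.7 × 12 = 9.6 weeks. At a = 10% the ratio is (0.2 + 0.90 × 9.6)/9.6 = 0.92. The sign therefore depends on which route out dominates.

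**Step 4: effect on the test.** Simulation assumptions: 60 per arm (half the planned 120), 0.3 events per patient-week, overdispersion 0.3-0.6, and 20% of prazosin v 5% of placebo patients leaving at week 2. Mean exposure is 10.0 v 11.5 weeks, so a true ratio of 1.30 appears as 1.30 × 10.0/11.5 = 1.13. With no true difference the t-test rejects in about 11-14% of trials, nearly always towards fewer events on prazosin. Adding drinking stops at pilot shares gives 9.09 weeks on prazosin and 0.05 × 2 + 0.95 × 7.2 = 6.94 on placebo. A true ratio of 1.0 then appears as about 9.09/6.94 = 1.31, and the t-test rejects in roughly 21-29%, now against prazosin.

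**Step 5: events that cluster early.** Section VI.A, item 2, reports from earlier use that adverse effects tend to come at the initial lower doses. With the 20% v 5% exits only, overdispersion 0.45, and 50, 70 or 90% of events in weeks 1-2, the t-test's false rejection falls to about 7.8, 6.0 and 4.9%. A true 1.30 appears as about 1.21, 1.26 and 1.29. A single log-exposure offset then fails: it falsely rejects in roughly 10-37%, against prazosin. In the extreme, if all events fall in weeks 1-2 and the true ratio is 1.5, dividing by total weeks gives 1.5 × 12/11.5 = 1.57 at 5% removal and 1.5 × 12/10 = 1.80 at 20%. A rate model split at week 2 stayed near nominal (4-8%) in every scenario tried.

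**Step 6: proportions.** At an assumed placebo rate of 0.1 per week, a true rate ratio of 1.5 and 9 v 12 weeks, the count ratio is 1.12 instead of 1.50, a factor of 0.75. The ratio of proportions with any event is 0.74/0.70 = 1.06 instead of 0.83/0.70 = 1.19, a factor of 0.89.

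**The case against.** A reader might infer that prazosin's event rate is understated, because intolerance removes prazosin patients early. The documents do not support that as a conclusion. The drinking rules in item 9 shorten exposure in the arm that drinks more. The pilot figures, and Hypothesis 2 for high-withdrawal patients, point to placebo, and Step 3 shows the bias then reverses. Intolerance removal is itself uncertain: a dose reduction comes first, most patients are expected to tolerate 16 mg, and Section VI would keep intolerant patients on a lower dose. The plan's 15-20% drop-out is not split by arm or cause.

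The reversed direction is no firmer. The pilot had 7 and 10 patients, and if relapsed patients stay on medication, as item 3 can be read, drinking shortens nothing.

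Other objections stand in part:

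- Inpatient-only treatment and early taper are not tied to arm in the text. Without an arm difference they add noise, not bias.
- A patient removed for intolerance has usually already had an event and stays in any proportion. Only later and repeat events are lost, but the plan does compare the number of events.
- Early clustering shrinks the bias and would make a simple constant-rate correction worse than the t-test.
- The comparison is not a powered safety test. That limits the severity; it does not justify ignoring exposure.

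The dropout control variable is no answer. It belongs to the mixed models for clinical outcomes, a t-test or chi-square takes no covariate, and three categories are not person-time.

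**Conclusion.** The concern holds for counts of adverse events, without a stated direction. The planned comparison ignores time on study, while the plan's own rules make that time unequal and partly dependent on treatment. Under a constant rate and the assumed exits, the observed ratio runs from 0.83 to 1.51 times the true one: towards fewer events on prazosin if intolerance exits dominate, towards more if drinking stops on placebo dominate. These figures rest on assumed removal shares, stop weeks and event rates, and on a very small pilot. The documents give no exposure by arm, so the real size cannot be stated. It is smaller if events come early, and smaller for the proportion with any event. This is a worthwhile, inexpensive correction to the analysis plan; it does not show that the safety result will be wrong.

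**What to change.** In the statistical section:

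1. Report weeks on study medication by arm, with the reason for stopping.
2. Compare event counts by negative binomial regression with log person-weeks as offset, split into weeks 1-2 and weeks 3-12. These match the periods before and after full dose already used in Data Analytic Procedures. Each patient contributes only the periods in which he or she was exposed. Include period and treatment setting as covariates and use standard errors robust to repeated periods per patient. Do not use a single constant-rate offset.
3. Show crude proportions with any event, by arm and type, alongside.
4. Count all events in the main analysis. Restrict to scheduled visits only as a sensitivity analysis, because the extra visits for continuing drinkers may raise detection.

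Two sets of statements must be reconciled, since they determine exposure: what follows drinking (item 3 against both parts of item 9), and what happens to patients who cannot tolerate the dose (item 3 against Section VI.A, item 3). Which rules apply is for the investigators to settle.

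The cost is some wording and slightly more programming. Start and stop dates of study medication are needed, and the documents do not say that these are recorded for analysis. The split model still assumes that, within a period, leaving is unrelated to a patient's further event rate, so the reasons for stopping should be read beside it.
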